C. Approach: This application will test the acute effects of 20 mg MEM (po) on EAIP in patients with mild-to-moderate severity AD (**Mini-Mental State Examination score between 10-22 at screening**), and determine whether sensitivity to MEM-induced changes in primary EAIP measures predicts the clinical response to MEM in these patients over a 24-week trial. The primary clinical outcome measure will be the Alzheimer's Disease Assessment Scale (ADAS-cog) (87), as described below. *Secondary analyses will assess alternate potential biomarkers, alternate outcome measures, and moderating roles of specific patient characteristics (including genotype), as well as the anatomical localization of the MEM-induced changes in EAIP measures.*

Aim 1. *To assess the acute effects of MEM (0 vs. 20 mg) on measures of early auditory information processing (EAIP) in patients with mild-to-moderate severity AD.* Measures of PPI, MMN and ASSR will be assessed in 88 individuals with mild-to-moderate severity AD after placebo (PBO) and 20 mg MEM po, in a double-blind, randomized order cross-over design. **Hypothesis 1:** Assessed across the full cohort of patients, PPI, MMN and ASSR will be significantly greater after MEM vs. PBO. However, the response to MEM will be heterogeneous: the magnitude of this “MEM effect” (MEM minus PBO) will vary across the dependent measures, and across patients, with some patients demonstrating robust increases in EAIP measures after MEM, and other demonstrating little response or reduced EAIP performance.

Aim 2. To determine the ability of MEM-induced alterations in EAIP in AD patients to predict their clinical response to MEM. The magnitude of the “MEM effect” will be calculated for each patient and each EAIP measure. MEM treatment will be initiated and titrated to 10 mg bid in all patients. Clinical severity will be assessed at baseline, 8, 16 and 24 weeks using the ADAS-cog as a primary measure. Analyses will determine whether the MEM effect on some or all EAIP measures moderates the magnitude of the clinical response to MEM. **Hypothesis 2:** Patients exhibiting a larger “MEM effect” on EAIP measures will exhibit a more robust positive clinical response to MEM, compared to patients exhibiting a smaller MEM effect on EAIP measures. This hypothesis will be tested empirically for each of the EAIP measures, and for regression-derived composite scores from multiple EAIP measures.

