Aim 1: Repeated measure (Rm)-ANOVAs will determine whether PPI, MMN and ASSR significantly differ after MEM vs. PBO (Hypothesis 1). Primary variables for each EAIP, as well as exploratory "secondary" measures, are identified above. Based on a recruited sample of 88 total participants, we will have 80% power to detect effect sizes of $d = 0.35$ (small) using a Bonferroni corrected $\alpha = .05/3$ (2-tail). Heterogeneity of response will be characterized using variance components expressed as intraclass correlation coefficients (ICCs).

Aim 2: Linear mixed-effects models regressing change in ADAS-cog outcome scores (at 8, 16, and 24 weeks vs. baseline) onto a fixed effect of group defined by MEM sensitivity will test the hypothesis that patients exhibiting a larger "MEM effect" on EAIP measures will exhibit a larger positive clinical response to MEM. Groups will be defined by a median split of "MEM effect" (MEM minus PBO) on EAIP. Power was estimated using methods described by Hedeker et al. (25) solving for sample size with $\alpha = .05$ (2-tail), test-retest correlations of .50, and 5% attrition at each time point. A sample of 88 total participants provides us with 80% power to detect a medium effect of $d = 0.50$. The primary outcome will be chosen based on effect sizes obtained as part of Aim 1. In exploratory analyses, we will also examine group by time interactions using orthogonal polynomial contrasts. We will also predict change in clinical outcomes as a function of all four candidate biomarkers in order to create an optimal prediction equation. We will perform ROC curve analyses using EAIP MEM sensitivity values as continuous variables and predict clinical improvement after MEM as a discrete outcome (responders vs. non-responders) in order to determine the clinical utility of this approach defined in terms of sensitivity and specificity. Secondary analyses will also be conducted with biomarker groups defined as "MEM-sensitive vs. -insensitive" via specific thresholds for EAIP MEM sensitivity.

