Multiple analytic strategies: The critical test of H2 will utilize both continuous and discrete analyses. Treating EAIP MEM sensitivity as a **continuous variable** will enable us to identify moderating factors (i.e. factors moderating the relationship between EAIP MEM sensitivity and clinical MEM sensitivity) with greater power. By identifying these moderators, and their relative contributions to the biomarker-clinical response relationship, *this continuous approach will potentially be more informative regarding the mechanisms by which EAIP MEM sensitivity is related to MEM's clinical impact*. Compared to ANOVA, a linear mixed-effects model is also relatively less impacted by missing data.

Treating MEM sensitivity as a **discrete variable** will enable us to divide the patient sample via a specific threshold, eg. median split, based on EAIP MEM sensitivity (Fig. 3). Exploratory analyses will test more or less stringent thresholds, aiming to optimize the positive and negative predictive value of this discrete threshold. *This approach has the potential practical value of establishing preliminary criteria for distinct MEM-sensitive and MEM-insensitive clinical subgroups.*

Secondary / Exploratory Analyses: To test H2, we will examine multiple metrics of **EAIP MEM sensitivity**:

1. **primary** measures from each individual EAIP measure (described above);
2. **secondary** composite variable based on these 4 primary measures, generated via multiple regression;
3. **exploratory** measures of EAIP: P3a amplitude and RON (described above).

An underlying premise of H2 is that the neurobiological bases of MEM effects on the Aim 1 EAIP measures share some amount of variance, and hence positive and negative predictive value, with the clinical therapeutic response to MEM in AD. However, MEM effects on these 4 EAIP primary measures likely reflects its actions on (overlapping but) non-identical neural substrates; this is consistent with findings that MEM sensitivities on these measures are positively correlated for some (MEM effects on MMN and ASSR (65)) but not other measures (MEM effects on PPI and MMN (99)). *Which of these primary measures, or composite measure, provides the best prediction of MEM effects on AD-relevant neural substrates, and hence provides the best prediction of MEM's therapeutic sensitivity, is an important empirical question that we will address in Aim 2.*

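### Aim 1's Bonferroni test is valid and meets its stated 80% power, but Holm's step-down would hold the same 5% family-wise error and raise power per measure to 86-88% if all three EAIP measures respond at d = 0.35

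*Combined protocol and SAP*

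**What the plan says.** Under *Statistical tests for each hypothesis*, Aim 1, the plan states: "Repeated measure (Rm)-ANOVAs will determine whether PPI, MMN and ASSR significantly differ after MEM vs. PBO". The data come from one group of patients, each tested under both conditions "in a double-blind, randomized order cross-over design". The power statement follows: "Based on a recruited sample of 88 total participants", the plan claims 80% power at d = 0.35, described as "small) using a Bonferroni corrected" alpha of .05/3, two-tailed.

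This is the only multiplicity statement for Aim 1. No step-down procedure is named, and no reason is given for single-step Bonferroni.

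Hypothesis 1 (*Specific Aims*, and again under *C. Approach*) is a claim about every measure: across the full cohort, "PPI, MMN and ASSR will be significantly greater after MEM vs. PBO".

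**The concern.** Read as the test rule, the statement holds each measure to .05/3 whatever the other two show. Holm's procedure orders the p-values. It compares the smallest with .05/3, the next with .05/2 and the largest with .05, and stops at the first failure. It controls the family-wise error at 5% under any correlation between the measures, and it can never reject less than Bonferroni.

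Bonferroni loses most when several effects are real, and that is what Hypothesis 1 predicts. At stake is how often a true effect on the second or third measure goes unreported in Aim 1, and how likely the plan is to confirm the whole of Hypothesis 1.

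**Working it through.** **Inputs from the plan.** n = 88, paired comparison, d = 0.35 (read as the standardized within-patient MEM-minus-PBO difference), three measures, family-wise alpha .05, two-sided.

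**Assumption.** The plan gives only the direction of the correlation between MEM effects, which are "positively correlated for some (MEM effects on MMN and ASSR (65)) but not other measures (MEM effects on PPI and MMN (99"). I use a common correlation of 0 to 0.5, with 0.8 as a check.

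**Step 1: the plan's own figure.** Noncentrality = 0.35 × √88 = 3.283, with 87 degrees of freedom. At .05/3 the critical t is 2.441 and power is **79.8%**, which matches the stated 80%. The detectable d at 80% power is 0.351. Reading the sample as two groups of 44 would give 23%, so the paired reading is the right one.

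**Step 2: Holm at correlation 0.** The same formula gives 84.0% at .05/2 (critical t 2.281) and 90.1% at .05 (critical t 1.988). Let x = 0.798, y = 0.840 − 0.798 = 0.042 and z = 0.901 − 0.840 = 0.061. These are the chances that a measure's p-value falls below .05/3, between .05/3 and .05/2, and between .05/2 and .05.

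- Power per measure = x + y[1 − (1 − x)²] + z(x² + 2xy) = 0.798 + 0.040 + 0.043 = **88.1%**.
- All three, Bonferroni = x³ = **51%**.
- All three, Holm = x³ + 3x²y + 3x²z + 3xy² + 6xyz = 0.508 + 0.080 + 0.117 + 0.004 + 0.012 = **72%**.
- At least one, either method = 1 − (1 − x)³ = 99.2%. The two agree because Holm's first step is the Bonferroni test.

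**Step 3: other correlations, by simulation of paired t-tests** (Monte Carlo error about 0.1-0.2 points), all three effects at d = 0.35:

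| Correlation | Per measure, Bonferroni | Per measure, Holm | All three, Bonferroni | All three, Holm | At least one, both |
|---|---|---|---|---|---|
| 0 | 80% | 88% | 51% | 72% | 99% |
| 0.3 | 80% | 87% | 57% | 75% | 97% |
| 0.5 | 80% | 86-87% | 61% | 77% | 95% |
| 0.8 | 80% | 85% | 68% | 81% | 90% |

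**Step 4: where the gain shrinks.**

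- Two real effects at d = 0.35: +3 to +3.5 points each.
- One real effect: about +0.1 point.
- All three real, correlation 0.3: +4.9 points at d = 0.20, +7.5 at 0.25, +8.7 at 0.30, +4.8 at 0.40 and +1 at 0.50.

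**Step 5: error rates under Holm.** The simulated family-wise error is 4.97% with no real effect, 4.1-4.7% with one real effect and 3.9-4.2% with two. In the last case only one null measure remains, and its false-positive chance rises from 1.7% under Bonferroni to about 4%.

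**Step 6: other family sizes and samples.** *Secondary / Exploratory Analyses* counts four primary EAIP measures, because ASSR contributes two. At .05/4, Bonferroni gives 76.6% per measure and Holm about 86-87% (correlation 0.3 to 0). If all 103 patients projected for EAIP tests in Table 2 are analysed, the figures for three measures are 86.6% and about 92.4% (correlation 0.3).

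**The case against.** The strongest reply is that nothing here is wrong. Bonferroni is valid and the plan reaches the power that it claims. This stands: a reader might infer that Aim 1 is underpowered or wrongly tested, and the documents do not support that. If all 103 patients with EAIP tests are analysed, the plan is above its target already.

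A reader might also take the gain of 6 to 8 points as unconditional. It is not. It needs all three effects to be real, near d = 0.35 and at most moderately correlated. The plan offers 0.35 as a detectable effect, not a predicted one. Hypothesis 1 itself expects the size of the effect to vary across measures, and the section asking whether Aim 2 depends on Aim 1 concedes that effects may be blunted in AD. The scenario remains fair because Hypothesis 1 predicts that every measure responds.

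Nor does Bonferroni buy nothing. It keeps the error on any single null measure at 1.7%, which matters when the question is which measure responds, and its tests and confidence intervals always agree. Under Holm, a measure with a p-value between .05/3 and .05 may be declared significant while its Bonferroni-width interval includes zero.

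Finally, a reader might think that Aim 2 is at risk. The plan says that neither the ability to test Hypothesis 2 nor its importance is reduced by a non-significant Aim 1. The choice carried from Aim 1 into Aim 2 is made on effect sizes, not p-values. The text under Fig. 10 names a biomarker characterization of each patient as the primary result of Aim 1, and that needs no significance test.

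One further caution stands. Bonferroni appears only in the power sentence, so reading it as the final test rule is a reasonable inference but still an inference. The same calculation would serve unchanged as the minimum-power statement under Holm.

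**Conclusion.** The point holds as an optional improvement in efficiency. The benefit lies wholly in the second and third measures, and so in confirming Hypothesis 1 as it is worded. The plan quotes only power per measure, so a reader cannot see that the chance of confirming all three is 51-61% at its own planning effect.

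The size of the gain rests on three conditions: all three effects at d = 0.35, 88 analysed pairs, and an assumed correlation of 0 to 0.5. Two results need none of these: Holm controls the family-wise error at 5%, and it never rejects less than Bonferroni. The consequence is confined to the reporting of Aim 1.

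**What to change.** In the Aim 1 paragraph, replace the Bonferroni test rule with: *Holm step-down across the primary EAIP measures, family-wise 5%, two-tailed*. Keep 80% at d = 0.35 as the minimum power per measure for three measures, and add that it is about 86-88% if all three respond at that size with correlation up to 0.5. If the family is settled at four measures, the minimum becomes 76.6%.

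State both downsides. The false-positive chance on a null third measure rises from 1.7% to about 4% when the other two respond, still within the family-wise limit. Bonferroni-width intervals may disagree with the Holm decision, so label them descriptive.

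Make the change before any Aim 1 data are analysed. The plan schedules looks at Aim 1 biomarker data at about 6 and 36 months, and a switch made after seeing p-values would not be credible. The cost is a few lines of wording, with no extra patients, visits or data.

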Phase 1 and Phase 2 measures will be used to achieve **2 Specific Aims**:

Aim 1. *To assess the acute effects of MEM (0 vs. 20 mg) on measures of early auditory information processing (EAIP) in patients with mild-to-moderate severity AD.* Measures of PPI, MMN and ASSR will be assessed in 88 individuals with mild-to-moderate severity AD after placebo (PBO) and 20 mg MEM po, in a double-blind, randomized order cross-over design. **Hypothesis 1:** Assessed across the full cohort of patients, PPI, MMN and ASSR will be significantly greater after MEM vs. PBO. However, the response to MEM will be heterogeneous: the magnitude of this “MEM effect” (MEM minus PBO) will vary across the dependent measures, and across patients, with some patients demonstrating robust increases in EAIP measures after MEM, and other demonstrating little response or reduced EAIP performance.

Aim 2. *To determine the ability of MEM-induced alterations in EAIP in AD patients to predict their clinical response to MEM.* The magnitude of the “MEM effect” will be calculated for each patient and each EAIP measure. MEM treatment will be initiated and titrated to 10 mg bid in all patients. Clinical severity will be assessed at baseline, 8, 16 and 24 weeks using the ADAS-cog as a primary measure. Analyses will determine whether the MEM effect on some or all EAIP measures moderates the magnitude of the clinical response to MEM. **Hypothesis 2:** Patients exhibiting a larger “MEM effect” on EAIP measures will exhibit a more robust positive clinical response to MEM, compared to patients exhibiting a smaller MEM effect on EAIP measures. This hypothesis will be tested empirically for each of the primary EAIP measures, and for regression-derived composite scores from multiple EAIP measures.

Analyses (linear mixed-effects model) will test the hypothesis (H2) that EAIP MEM sensitivity (in Phase 1) predicts the clinical response to MEM (in Phase 2). Moderating roles of specific variables on MEM sensitivity will be assessed, including demographic/clinical variables, baseline neuropsychological measures and genotypes associated with MEM sensitivity or AD. Source localization will identify anatomical substrates associated with MEM effects on EAIPs, and enable us to test structure- and circuit-based mediation models.

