PPI is generally viewed as a measure of automatic, preattentional inhibition (17). It is regulated by circuits connecting portions of the prefrontal and mesial temporal cortex, with subcortical systems extending from the basal ganglia to the pons (101). Drugs acting at prominent nodes in this circuitry have potent effects on PPI (108). For example, PPI is **increased** in HS by the NMDA antagonists ketamine (1,15), amantadine (105) and MEM (107). We first reported the PPI-enhancing effects of MEM (20 mg po) in HS (107); these findings were extended as seen in Fig. 2. MEM (20 mg) significantly increased PPI in SZ patients (Fig. 2A), across 10-120 ms prepulse intervals; comparable effects were detected in HS at 60 ms intervals, which is a critical “sensitive” temporal window for therapeutic drug effects (103). Interestingly, these potent MEM effects in SZ patients were evident despite the fact that, as a group, these patients were not deficient in PPI, consistent with the fact that 90% were taking PPI-normalizing second generation antipsychotics (SGAPs) (48,103,123).

[figure not shown]
MEM effects on PPI are moderated by age and baseline PPI level, but not by AP load, anticholinergic load or demographic or clinical variables (5,99). These findings support the strong prediction that PPI will be a potent signal of MEM “bioactivity” in this application – a quantifiable measure of MEM’s activity within the brain, and specifically within PPI-regulatory circuitry that includes elements relevant to the pathophysiology of AD - and might conceivably serve as a “biomarker” predicting therapeutic response to MEM among AD patients.

2. **MMN** is an auditory event-related potential (ERP) component 50-150 ms after a deviant, “oddball” stimulus is presented within a sequence of repetitive standard sounds (Fig. 5: shown, from mild-to-moderate AD patients, n=20 ([name])); it reflects the properties of automatic, memory-based comparison processes (cf. 74). It is rapidly assessed, and while it is highly stable in normal and impaired patient populations across the lifespan (63), studies of this form of MMN in AD patients have reported inconsistent results, with many studies reporting no differences vs. age-matched HS (21,76-7). MMN is largely automatic and preattentional, yet it is strongly associated with neurocognition and psychosocial function, even in HS (64).

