Design Overview: The general study design is modeled after that employed by Peskind et al. (79) and Pomara et al. (81). These authors conducted a 24-week, multi-site placebo-controlled randomized trial of MEM monotherapy (10 mg bid) in mild-to-moderate AD, demonstrating significant gains in cognitive, global and behavioral measures. The present study will differ from that of Peskind et al. (79) in 3 major ways: 1. Patients will be characterized at baseline to assess their EAIP response to a MEM “challenge dose” (20 mg); 2. This is a single site study; 3. All patients will receive MEM treatment; to test the key hypothesis (H2), analyses will compare groups stratified by the magnitude of their EAIP response to MEM. Other minor methodological differences will be described below.

88 AD patients who consent to participation undergo a full neurocognitive characterization and medical evaluation. Patients also receive baseline ADAS-cog assessment and secondary outcome measures (described below) by [name] (Neuropsychologist; Clinic Director: UCSD Memory, Aging and Resilience Clinic [MARC]; Co-I).

Patients will then be tested in a PBO-controlled double-blind within-subject cross-over study of the effects of 20 mg MEM po on EAIP measures (PPI, MMN, ASSR). This proposed “N” is adequate to be stratified into “low” vs. “high” MEM sensitivity using discrete criteria, eg. median split, for categorical analyses (eg. ANOVA) and to detect medium effect size ($d=0.5$) differences in outcome between MEM-sensitive vs. -insensitive patients (see “Power Considerations”). Inclusion and exclusion criteria are seen in Table 2.

Table 1. Inclusion and exclusion criteria

Inclusion: 1. ADRC-confirmed diagnosis of AD; 2. **MMSE score 10-22**; 3. Age 50-70 y; 4. Knowledgeable caregiver; 5. Ambulatory; 6. Medically stable; 7. Audiometric testing (detection ≤ 40 db(A) at 1000 Hz); 8. Informed consent.

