Analyses to test H2 will also utilize primary, secondary and exploratory metrics of **MEM's clinical effects**:

1. **primary** outcome measure: ADAS-cog, change from baseline;
2. **secondary** outcome measures: NPI-Q and Geriatric Depression Scale (change from baseline);
3. **exploratory** outcome measures: ADAS-cog factor-derived subscales (change from baseline) (eg. 81).

Factors that moderate the relationship of the primary biomarkers (EAIP MEM sensitivity) and clinical outcome will also be explored, including: 1. Genetic markers (GRIN, APOE, described above); and 2. Patient characteristics (eg. age; past AD medications; baseline (T0) neuropsychological and outcome measures).

Lastly, we will probe the specific anatomical basis of MEM effects on MMN and ASSR using **source locali-**

zation techniques (109,124); conceivably, these analyses will provide information more generally relevant to the anatomical basis for MEM's therapeutic actions, i.e. the "mediators of the therapeutic intervention", as described in this PAR. A simple model for such mediation might be: "MEM action on 'structure X' → EAIP change → enhanced therapeutic sensitivity," but more complex, circuit-based models will also be explored.

For simplicity, this application associates greater "EAIP MEM sensitivity" with an EAIP-enhancing response to MEM challenge (eg. EAIP (MEM minus PBO) > median value); this approach is parsimonious because arithmetically larger EAIP values are generally associated with positive neurocognitive and functional change (21,56,58,64,111). However, one might rationally argue that *any significant change in response to MEM challenge reflects "MEM sensitivity", and thus directionality of the MEM response should not be assumed*. Thus, while we represent arithmetically larger MEM responses as "MEM-sensitive" in this application, Aim 2 analyses (linear mixed-effects model) make no assumptions of directionality; exploratory categorical analyses will also define "MEM sensitivity" based on the absolute change in EAIP amplitude (i.e., positive or negative).

Important questions related to experimental design and analysis:

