Sex as a biological variable: Sex will be included as a grouping factor in all major analyses; groups will be sex balanced as described in "Human Subjects". The PI was the first to report sex differences and menstrual cyclicity of PPI in HS (102), and some EAIP sex differences may persist into late life (48). No sex differences in **MEM effects** on PPI, MMN (99) or ASSR (65) were noted in our studies (Fig. 2).

Timeline (Table 2): Screening 114 subjects/57 mo. (2 subjects / mo.) is well within the capacity of our referral sources in the UCSD Memory and Geriatric Medicine Clinics, ADRC and affiliated community network (cumulative flow >>15 new AD patients/wk). Proposed EAIP testing rate (< 4 tests / mo.) is well within our capacity (typical rate 16 tests / mo.). Thus, subject recruitment and test rate should meet the demands of the proposed "N". EAIP methods are currently in use in our lab, so no new training, equipment or infrastructure is needed. At a rate of ≈1.5 completed subjects/mo., we will reach our target in 57 months, leaving 3 months for genotyping, data analysis and writing. Interim analyses at ≈6 months will confirm the fidelity of all measures and potentially adjust MEM test dose (see above), and at 36 months will guide a future NIA application.

Key benchmarks of success will include: 1. Recruitment and clinical and neurocognitive assessment of 88 individuals with Mild-to-Moderate AD (M:F ≈ 44:44). 2. Completion of two days of EAIP testing in study subjects, one week apart, in a double-blind, cross-over design using PBO vs. 20 mg MEM. 3. Titration of MEM to target dose (10 mg bid). 4. Repeated clinical and neurocognitive assessment after 8, 16 and 24 weeks of MEM treatment. 5. Completion of proposed analyses of EAIP and clinical data to test hypotheses, H1 and H2.

Potential Limitations:

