1. Recruitment: One concern is the possible difficulty recruiting sufficient numbers of individuals with mild-to-moderate severity AD. A strength of this application is its intimate ties to active AD clinics and ongoing studies with large samples of well-characterized older adults, many of who have been diagnosed with AD, through collaborations with the UCSD Memory Clinic and Geriatric Medicine Outpatient Clinic, the UCSD ADRC and its affiliated networks throughout San Diego. Recruitment needs for this application are ≈ 2 new subjects / mo. (see "Timeline" and Table 2), with a projected 10% attrition at screening, and 5% attrition at each of the subsequent points of study contact (EAIP testing, weeks 8, 16 and 24), based on past experience and ongoing studies. The target population (mild-to-moderate AD) is not a focus of most ongoing UCSD studies, which prioritize MCI and Pre-MCI subjects; thus, availability of AD patients for this application will support much higher recruitment needs if attrition exceeds projected rates.

2. EAIP measures in AD patients: Our published reports of MEM effects on EAIP measures involved HS and SZ patients, ages 18-55 (65,99). The present application proposes such measures in patients with mild-to-moderate severity AD, ages 50-70 y; thus, both diagnosis and age of the proposed cohort differ from our past experience, and may present unexpected challenges. Importantly, our laboratory group has published extensively on EAIP measures across the full lifespan (eg. ages 18-88: (16)), and in populations with severe dementia and behavioral disturbances (eg. Huntington's Disease (104)), and recently completed a study of EAIP measures in 20 patients with mild-to-moderate severity AD ([name], PI). Thus, neither the clinical symptoms nor age of the proposed cohort should limit the acquisition or interpretation of EAIP measures.

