8. Assist the NIA by commenting on any problems with study conduct, enrollment, sample size, and/or data collection.
9. Considering the overall picture, including need to pursue both primary and appropriate secondary analysis, and making these recommendations during the data analysis phase of the project;
10. Reviewing final results, via DSMB report by PI within 90 days of completion of final study subject.

Inclusion of Women and Minorities

Inclusion of women: Women will be included in this study. One key dependent measure (PPI) exhibits clear sexual dimorphism; previous studies of memantine effects detected **no interactions of sex with drug or diagnosis** for any of the proposed measures of early auditory information processing (PPI, MMN or ASSR). Importantly, it is possible that a significant effect of memantine on auditory processing measures, or an interaction between memantine sensitivity and potential moderating factors (e.g. age, baseline performance, single nucleotide polymorphisms) will be evident in only one or the other sex, or that relationships among specific measures might be sex-specific. Thus, there is a strong rationale for assessing the predicted drug effects in both men and women, to test specific predictions of drug-behavior relationships.

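### The powered H2 model compares biomarker-defined, non-randomised groups in one treated arm with sex but not age as a factor, so a positive H2 could partly reflect age

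*Combined protocol and SAP*

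**What the plan says.** **The model.** Under Statistical tests for each hypothesis, Aim 2 is a linear mixed model of ADAS-cog change "at 8, 16, and 24 weeks vs. baseline) onto a fixed effect of group defined by MEM sensitivity". Groups are formed by a median split of the MEM minus placebo difference on an EAIP measure. No covariate is named there or in the general statistical approach. The section on sex as a biological variable adds one factor: "Sex will be included as a grouping factor in all major analyses".

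**The design.** All patients receive memantine. The section explaining the lack of a control group confirms that there is no parallel AD treatment group, and the Data and Safety Monitoring Plan confirms that the comparison rests on groups defined by the biomarker.

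**Age and the MEM effect.** The PPI paragraph of Measures of EAIP reports: "MEM effects on PPI are moderated by age and baseline PPI level, but not by AP load, anticholinergic load or demographic or clinical variables". Inclusion of Women and Minorities raises the possibility of "an interaction between memantine sensitivity and potential moderating factors (e.g. age, baseline performance, single nucleotide polymorphisms" being sex-specific. That sentence names age but reports no finding.

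**Where age is analysed.** Specific Aims: "Moderating roles of specific variables on MEM sensitivity will be assessed, including demographic/clinical variables, baseline neuropsychological measures". Secondary / Exploratory Analyses lists, among moderators of the biomarker-outcome relationship, "Patient characteristics (eg. age; past AD medications; baseline (T0) neuropsychological and outcome measures".

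**Populations.** Potential Limitations, item 2: "Our published reports of MEM effects on EAIP measures involved HS and SZ patients, ages 18-55". Table 1 of this trial: "3. Age 50-70 y; 4. Knowledgeable caregiver".

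**The concern.** H2 is a comparison of observational strata, so a factor linked both to the MEM effect and to ADAS-cog change can produce a group difference unrelated to memantine response. The plan itself singles out age for the first link, at least for PPI. Age is collected, yet it is not in the model that was powered.

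The planned age analyses do not fill the gap. Testing age as a moderator asks whether the biomarker-outcome slope differs by age. It does not adjust the group effect. The Specific Aims analysis may show whether age and MEM sensitivity are related, but nothing carries that result into the H2 comparison.

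The stake is how a positive result is read. The Significance section foresees steering marker-negative patients towards other treatments, which presupposes that the marker concerns memantine response. The section on the missing control group considers that the marker might predict response to other drugs as well. It does not consider that the marker might predict clinical course whatever the drug.

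**Working it through.** **1. The plan's own power figure.** Inputs from the Aim 2 text: N = 88 (44 per group), d = 0.50, two-sided alpha .05, test-retest correlation .50, 5% attrition per time point. With three post-baseline visits and compound symmetry, the information per patient is I = sum of p_k × k/(1 + (k−1)ρ), where p_k is the share of patients with exactly k visits.

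- Retention 1, .95, .9025: I = .05×1 + .0475×1.333 + .9025×1.5 = 1.467. Mean z = 0.50 × sqrt(44 × 1.467/2) = 0.50 × 5.681 = 2.84, so power = Φ(2.84 − 1.96) = 81%.
- Attrition already at week 8 (.95, .9025, .857): I = 1.394, mean z = 2.77, power 79%.

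The stated 80% reproduces.

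**2. Spurious effect when age is left out.** Let r1 be the correlation of age with the MEM effect and r2 that of age with ADAS-cog change at each visit. No document gives either, so all values are assumptions. With no true group effect, the split shows d = 2 × sqrt(2/π) × r1 × r2 = 1.596 × r1 × r2. Mean z = 5.681 × d, and the rejection rate is Φ(z − 1.96) + Φ(−z − 1.96).

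**3. Narrower age range.** The age evidence comes from samples aged 18-55; this trial takes 50-70. With uniform ages (assumed), SD = range/sqrt(12): 37/sqrt(12) = 10.68 and 20/sqrt(12) = 5.77 years, ratio u = 0.54. At the same slope, r1' = r1×u/sqrt(1 − r1² + r1²u²). Values of .1, .2, .3 and .4 in the earlier samples become .05, .11, .17 and .23.

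Worked cell, r1 = .3 and r2 = .3: d = 1.596 × .168 × .3 = 0.080; z = 0.456; rejection = Φ(−1.504) + Φ(−2.416) = 7.4%.

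False-positive rate of the median split, age omitted, ages 50-70:

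| r1 at 18-55 (r1' at 50-70) | r2 = .1 | r2 = .2 | r2 = .3 | r2 = .4 |
|---|---|---|---|---|
| .1 (.05) | 5.0% | 5.1% | 5.3% | 5.4% |
| .2 (.11) | 5.1% | 5.5% | 6.0% | 6.8% |
| .3 (.17) | 5.3% | 6.1% | 7.4% | 9.3% |
| .4 (.23) | 5.5% | 7.0% | 9.6% | 13.2% |

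Simulation (N = 88, three visits, visit and sex in the model) of the four cells with both links at .3 or .4 gave 7.8% to 12.9% without age and 5.2% to 5.8% with it. For the continuous predictor, divide z by sqrt(2/π) = 0.798. The .3/.3 cell becomes about 9% and the .4/.4 cell about 18%.

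**4. Power cost of adding age (d = 0.50).**

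- Age unrelated to biomarker and outcome: simulated power is 79.6% without age and 79.7% with it, a loss of 0-1 point.
- Age related only to the biomarker: z shrinks by sqrt(1 − (2/π) r1²). From 81.1%, power falls to 80.1%, 78.8% and 76.8% at r1 = .2, .3 and .4, a loss of 1.0, 2.3 and 4.3 points. Simulated losses were 1.5 to 4.1 points, so an allowance of 2-5 points is prudent.
- Age related only to ADAS-cog change at .2 or .3: simulated power rises by about 2 or 6 points.

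**The case against.** **One link is undocumented.** Confounding needs age to be related to both the MEM effect and ADAS-cog change. The documents give the first for PPI only, without size or direction, in samples without AD, and they do not give the second at all. The plan also lets Aim 1 effect sizes guide the choice of primary for Aim 2. If that leads to MMN or ASSR, no documented age link applies. This stands, and it is why the size is stated as a range under assumptions.

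**Marginal against conditional claim.** H2 as written is marginal: patients with a larger MEM effect should do better. If age drives both quantities, the marker still predicts course on memantine, and rejecting the marginal null is not an error. This stands in part. It is a reason to report the unadjusted estimate too, but it does not support reading a positive H2 as memantine sensitivity.

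**Partly handled already.** A moderator model would ordinarily contain an age main effect. The text does not say so, and those analyses are exploratory.

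**Limited remedy.** Age adjustment cannot separate prediction of memantine response from prognosis without a comparison arm. This is correct, and it is why the fix also limits the wording of the claim.

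**Uneven treatment of severity.** Age might act through the same spared or damaged circuitry that the plan treats as part of the biomarker. That is possible, but the plan makes the circuitry argument for disease-related damage, not for age.

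**Conclusion.** The point holds in a limited form. The powered H2 model omits a collected variable that the plan itself says moderates one of its four primary biomarkers, in a comparison that randomisation does not protect. If age also relates to ADAS-cog change, a positive H2 could partly reflect age. Because the direction is unknown, age could equally mask a true association.

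For ages 50-70, the split's false-positive rate would be about 5-7% for assumed correlations of .1 to .3 on each link, and up to about 13% at .4 on both. With age in the model it is about 5%. These figures rest on assumed correlations, uniform ages and an unchanged slope.

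Three stronger readings are not supported:

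- A reader might infer that H2 is badly inflated. Without the age-range restriction, .4 on both links gives 30.6%, but that carries a strong link over unchanged from a wider age range and adds an age-outcome link that no document shows.
- A reader might infer that the power calculation is wrong. It reproduces.
- A reader might infer that baseline ADAS-cog must also enter the main model. The plan makes spared or damaged circuitry part of its hypothesis, so a raw-change model is defensible.

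**What to change.** 1. In the Aim 2 text, pre-specify age, with sex and visit, as a covariate in the ADAS-cog change-score mixed model, for both the median-split and the continuous predictor. Report the estimate without age beside it.
2. Word a positive H2 as an association between the MEM effect and clinical course on memantine.
3. In the section on the missing control group, add that the marker may reflect prognosis regardless of drug, and that adjusting for age does not resolve this.

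A sensitivity analysis that also adjusts for baseline ADAS-cog is optional and separate from this point.

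The cost is SAP wording and one degree of freedom: about 0-1 point of power, or about 2-5 points if age correlates .2-.4 with the biomarker and not with the outcome. No new data and no change to the 88 patients are needed. The headline claim becomes narrower.
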